12. DATA AND SPECIMEN BANKING*

No specimens will be banked for future use. See #13, Data Management, for data retention and access.

13. Data Analysis and Management*

Responsibility for 6 month and 12 month outcome data collection was transferred from UMMS to Northwestern during 2021. At the completion of study enrollment (on or about March 1, 2022), the UMMS data enrollment and collection services will be completed. At that date, the UMMS data center will have already, or will then, transfer all enrollment, patient-reported, and study data to Northwestern for the analytic team to manage and analyze. The UMMS data center will confirm that they expunged all ASK study data from the web-based data capture systems (DatStat, RedCap) and UMMS data storage files within UMMS.

Aim 1

We will transcribe recorded interviews and code using content analysis techniques to identify themes. We expect to achieve data saturation at or before completing 30 interviews with patients and 30 with caregivers.

AIM 2 and 3. Sample size and effect size estimates:

The trial is designed with $\geq 80\%$ statistical power at 5% significance level to detect intervention effects that are meaningful to both patients and surgeons, and health systems. In total, 40 (Aim 2) or 54 (Aim 3) surgeons will be randomized equally to treatment and control arms with an average of 100 patients/surgeon. Based on data from FORCE-TJR, the intraclass correlation within surgeon is approximately 0.02. Using two independent group t-tests adjusting for within surgeon clustering, the trial can detect an intervention effect of (a) improved decision quality of >0.16 SD ; (b) improved quality of OA care defined in two ways: 6 month post-decision pain relief (KOOS/HOOS) of ≥ 3.3 points for TKR patients (34.1 vs. 37.4; SD=20.8) and ≥ 3.3 for THR patients (45.7 vs. 49.0; SD=20.9) or greater proportion of patients with meaningful pain relief (17 points in HOOS/KOOS pain score) of $\geq 6.1\%$ more TKR patients (77.9% vs. 84.0%) and $\geq 4.2\%$ more THR patients (90% vs. 94.2%).

Aims 2 and 3: Overview of analytic approach. We hypothesize (Aim 2) that patient/clinician use of the OA Careplan will improve decision quality as well as

INVESTIGATOR STUDY PLAN

12.14.2021

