will be entered into the same model in order to assess their contributions to the outcome under analysis, after adjusting for each other, as well as the patient-level covariates. Model assumptions will be carefully examined. In these model-building processes, effect modifications will be examined by including interaction terms between relevant covariates, and to ensure the heterogeneity of the intervention effects among patient subgroups are adequately considered. The analyses will be conducted with all patients; and then for TKR and THR patients separately. While the primary goal is to understand patient-level covariates with outcomes, it is critical to assess surgeon/site factors that may influence outcome for all, or sub-groups of patients. For example, obese, diabetic patients with cardiac disease may have more positive decision quality and pain relief with a more experienced high-volume surgeon.

Aim 2: To assess the effect of OA Careplan on (a) decision quality and (b) pre-to- post decision pain relief and functional gain, we will do the following. We expect 20 surgeons and 2000 patients will receive the OA Careplan intervention, and another 20 surgeons and 2000 patients will receive usual care. The analyses will be conducted with all patients; and then for TKR and THR patients separately. First, we will tabulate the decision quality and care outcomes by arm and for select patient subgroups (e.g., sex, age, race/ethnicity). Second, we will use GLLAMM to estimate adjusted Careplan intervention effects by including in the models a Careplan indicator (Careplan intervention=1 vs. usual care=0) and a set of site/surgeon and patient variables for adjustment. A statistically significant coefficient of the Careplan indicator signals possible intervention effect. In this analysis, interaction terms between the Careplan indicator and surgeon or patient factors will be examined, statistically significant interaction terms may suggest the existence of heterogeneity in intervention effects. If present, intervention effects will be analyzed and presented by subgroups.

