Second, we will use GLLAMM to analyze the differences in joint pain and function at 6 and 12 months after the care decision between OA Careplan and comparison arms. We will pool data from both arms in the two phases. We will include an indicator variable to represent intervention status (usual care, OA Careplan, or OA Careplan+Support). We will assess whether 6 and 12 month pain differ between intervention arms. Next, we will repeat this process for the patients with meaningful (>17 point) change in HOOS/KOOS pain score. We expect pain relief will be significantly improved in the OA Careplan arm, with greater improvement to occur in the OA Careplan+Support, compared to the usual care group. Finally, we will formally test the mediation effects of Careplan and Careplan+Support on pain relief and functions at 6 and 12 months, using the two level structural equation models with mediation effects by Krull and MacKinnon (2001) and Preacher, Zyphur and Zhang (2010).

Only those listed in our IRB application will have access to identified data.

At this time, there is no plan to destroy the Patient Reported Outcome (PROs) data because of the value to this data regarding national norms for PROs for patients electing to have surgery and those electing non-surgical management of OA.

PHI including individual contact information for follow-up date collection will be destroyed after all surveys have been completed by individual patients 3 years after the completion of the study.

Published data derived from this study will consist of statistical analyses collapsed (averaged) across participants. Under no circumstances will data from individual participants be identifiable in reports or published manuscripts.

INVESTIGATOR STUDY PLAN

12.14.2021

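### Careplan versus usual care on 6- and 12-month pain and function is analysed both in the randomised Aim 2 data and in data pooled over both phases, without saying which analysis the conclusion rests on

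*Combined protocol and SAP*

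**What the plan says.** Section 4 (Aim 2) and section 10 (item 1) ask whether the Careplan improves pain relief and functional gain over usual care. Section 4 sets the times at 6 and 12 months.

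The Aim 2 paragraph of section 13 answers with a mixed model containing a 1/0 Careplan indicator, and reads the result this way: "A statistically significant coefficient of the Careplan indicator signals possible intervention effect". The sample-size text in section 13 is built for a comparison of this kind: "Using two independent group t-tests adjusting for within surgeon clustering". It gives the only error rate in the plan: "statistical power at 5% significance level to detect intervention effects".

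The Aim 3 text of section 13 ends with a second model for joint pain and function at 6 and 12 months. Here "We will pool data from both arms in the two phases", and the listed term is an intervention status with three levels: usual care, Careplan, and Careplan plus Support. The stated expectation is "We expect pain relief will be significantly improved in the OA Careplan arm", with a larger gain under Careplan plus Support, both relative to usual care.

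The same Aim 3 text says that surgeons who gave usual care in Aim 2 give the Careplan in Aim 3, that the Aim 2 Careplan surgeons move to Careplan plus Support, and that further surgeons are added. No section ranks the two analyses or calls either one supportive.

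**The concern.** The two analyses address the same effect on the same outcomes at the same times, but they do not estimate it in the same way. The Aim 2 comparison is concurrent and randomised. In the pooled model, usual care exists only in phase 1 (Aim 2) and Careplan plus Support only in phase 2 (Aim 3), while Careplan patients come from both. Part of the pooled Careplan-versus-usual-care estimate therefore sets later patients against earlier ones, often patients of the same surgeons.

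Without a phase term, any change over time in case mix or outcomes enters that estimate as if it were a Careplan effect. The documents give reasons to expect change. Section 6 widens Aim 3 eligibility beyond patients new to the practice and drops non-English speakers. Section 8 adds Covid-19 measures from about September 2020.

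If the two results differ, the plan does not say which one the Aim 2 conclusion follows. A null randomised comparison could stand beside a significant pooled one, and a reader could not tell which was meant to count.

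**Working it through.** **Inputs from section 13:** 20 + 20 surgeons in Aim 2, 100 patients per surgeon, ICC 0.02, SD 20.8 and a 3.3-point difference (TKR pain), 5% significance. Section 4 gives the current size of 3,000 patients per aim, which is 75 per surgeon with 40 surgeons. It also gives 36-40 surgeons for Aim 3.

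**My assumptions:** two-sided tests, a surgeon effect that is constant across phases, and the numbers of surgeons and patients carried into Aim 3.

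**1. The plan's own figure.** Design effect = 1 + 99 × 0.02 = 2.98. Effective n per arm = 2000/2.98 = 671. SE = √(2/671) = 0.0546 SD. Power for 3.3/20.8 = 0.159 SD is Φ(0.159/0.0546 − 1.96) = 82.8%, or 80.8% by noncentral t with 38 df. The stated 80% or more is reproduced, and it belongs to a two-group contrast of the Aim 2 kind. At 75 per surgeon the design effect is 2.48, effective n is 605, SE is 0.0575 SD and power is 78.8%.

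**2. The pooled estimate, all 40 surgeons carried over, 75 patients each per phase, no phase term.** Work in SD units. Let τ = 0.02 be the surgeon variance and e = 0.98/75 = 0.0131 the residual variance of a surgeon's mean. A1 and A2 are the mean outcomes of the former usual-care surgeons in phases 1 and 2. B1 is the phase-1 mean of the Careplan surgeons. Their phase-2 mean only informs the Careplan plus Support level.

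- Pooled Careplan minus usual care = w·A2 + (1 − w)·B1 − A1.
- The least-variance weight is w = (2τ + e) / (2(τ + e)) = 0.0531/0.0661 = 0.80. So about 80% of the weight on the Careplan side comes from phase-2 patients.
- Variance = [(τ + e)(w² + (1 − w)² + 1) − 2wτ]/20 = 0.00118, so SE = 0.0343 SD.
- Aim 2 estimate = B1 − A1, with SE = √(2 × 0.0331/20) = 0.0575 SD.
- Correlation of the two estimates = 0.0343/0.0575 = 0.60.

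**3. Chance that at least one is significant with no effect.** This is 1 − P(|Z₁| ≤ 1.96 and |Z₂| ≤ 1.96) for a bivariate normal. With correlation 0.60 it is 8.8%. Independent tests would give 1 − 0.95² = 9.75%.

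**4. Drift between phases.** A shift d in phase 2 biases the pooled estimate by w·d. For d = 0.05 SD (0.05 × 20.8 = 1.04 points), 0.80 × 0.05/0.0343 = 1.17, and P(|Z + 1.17| > 1.96) = 22%. The Aim 2 comparison is unaffected.

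**5. Other carry-over assumptions**, by the same generalised least squares:

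| Aim 3 surgeons; patients per surgeon (Aim 2 / Aim 3) | Phase-2 weight | Correlation | Either significant, no phase term | Either significant, phase term | Pooled test alone, 0.05 SD drift, no phase term |
|---|---|---|---|---|---|
| 40 carried over; 75/75 | 80% | 0.60 | 8.8% | 5.0% | 22% |
| 40 carried over; 100/100 | 84% | 0.55 | 8.9% | 5.0% | 29% |
| 40 carried over + 14 new; 100/100 | 85% | 0.55 | 8.9% | 6.6% | 30% |
| 20 carried over + 18 new; 75/79 | 69% | 0.69 | 8.4% | 6.5% | 14% |
| 0 carried over, 38 new; 75/79 | 49% | 0.87 | 7.3% | 5.0% | 8% |

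The fourth and fifth numeric columns assume no drift. With a phase term, the correlation between the pooled and Aim 2 estimates rises to between 0.94 and 1.0.

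**The case against.** The documents already place this question. Careplan versus usual care is Aim 2, it is item 1 of the endpoints, and it has its own analysis paragraph. The pooled model closes the text on Careplan plus Support. The natural reading is that Aim 2 answers the question and the pooled model is a later combined analysis. That is a fair inference, but it is only an inference. The pooled text states its own expectation of significant improvement over usual care and carries no supportive label.

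A reader might go further and infer that the plan sets up two deciding tests, so that success can be declared on either at 5%. The documents do not support that. The Aim 2 wording speaks of a possible effect, the pooled wording of an expectation, and neither is a success rule. The 5% appears only in the sample-size text.

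A reader might also infer that the pooled estimate is mostly a same-surgeon before-after comparison. That depends on carry-over, which is uncertain. The Aim 3 text moves all 40 surgeons on and adds more, section 4 gives a total of 36-40, and section 8 says that Careplan surgeons will be invited. If none carried over, no same-surgeon comparison would remain.

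Finally, a phase term could be added under the plan's general covariate provisions, and it would remove most of the problem. The pooled model does not list one, and neither do the candidate covariates.

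**Conclusion.** The point holds as a gap in specification with a real consequence. One effect is analysed in two data sets, the analysis that supports the conclusion is not named, and one of the two is partly non-concurrent.

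With no drift, the excess false-positive risk is modest: about 7% to 9% against 5% for one outcome at one time point, and about 5% to 6.6% with a phase term. The larger exposure is drift in a pooled model without a phase term. An assumed 0.05 SD raises the pooled test's own rejection rate to between 8% (no carry-over) and 22% (full carry-over) at 75 to 79 patients per surgeon, and to 29% or 30% at 100.

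The carry-over, the drift, the two-sided tests and the patients per surgeon in each phase are assumptions. The structural gap does not depend on them.

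The pooled estimate is more precise, so under a true effect the two analyses would often differ in significance. That would mostly reflect unequal power and should not be read as a rate of false claims.

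**What to change.** In the Aim 2 paragraph of section 13, state that the conclusion on Careplan versus usual care for pain and function rests on the concurrent Aim 2 comparison, using Aim 2 patients only and arms as randomised.

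In the pooled analysis at the end of the Aim 3 text:

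- add a phase (Aim 2/Aim 3) term;
- label the contrasts of Careplan and of Careplan plus Support with usual care as supportive, reported as estimates with confidence intervals;
- reword the expectation of significant improvement to match.

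This is a wording change with no new patients or data. Power of the Aim 2 comparison is unchanged at 82.8% with 2,000 per arm, or 78.8% with 1,500. The small cost is that the more precise pooled estimate (0.034 against 0.058 SD without a phase term) cannot carry the claim alone. Letting both analyses decide at 2.5% each would cost more: Aim 2 power falls to 74.7% or 69.8%.

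The change brings one outcome at one time point back to 5%. It does not settle multiplicity over outcomes, time points or joints.

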14. PROVISIONS TO MONITOR THE DATA TO ENSURE THE SAFETY OF SUBJECTS*

Not applicable as this is a minimal risk study.

15. WITHDRAWAL OF SUBJECTS WITHOUT THEIR CONSENT*

Not applicable

16. RISKS TO SUBJECTS*

For participants participating in Interviews, a possible risk is that some questions we ask during the interview could make participants upset. This is highly unlikely as we will be asking about opinions, however participants will be encouraged to skip any question they do not want to answer or stop the interview at any time.

No risks are anticipated to the health or wellbeing of the patient participating in this study. The OA Careplan (with or without support) are based on best practices of decision support. However, a theoretical risk to confidentiality exists whenever data are collected for research. All means possible will assure that the patient reported data remain anonymous and confidential in any future analysis or reports. There have been no documented confidentiality breaches in the prior UMMS Orthopedic studies. However, there is a rare chance that one

INVESTIGATOR STUDY PLAN
12.14.2021

could occur.

If a breach of the database releases identifiable information, the participating surgeons and the sponsor (PCORI) will be notified immediately. However, we have a protocol to minimize or prevent a breach in confidentiality, including keeping the patient identifiers separate from the analytic dataset. Data management strategies meet HIPAA and research privacy and confidentiality standards. However, if any unanticipated problems or adverse events occur, these will be reported to the UMass IRB as per policy.

17. POTENTIAL DIRECT BENEFITS TO SUBJECTS*

NA

18. VULNERABLE POPULATIONS*

NA

19. MULTI-SITE RESEARCH*

All recruitment methods are local.

See #8 above.

20. COMMUNITY-BASED PARTICIPATORY RESEARCH*

NA

21. SHARING OF RESEARCH RESULTS WITH SUBJECTS*

We will not be sharing research results with individual subjects.

22. SETTING

See #8 above

23. RESOURCES AVAILABLE

Staff training: All project staff will pass the CITI exam on ethical conduct of research. Any newly hired study staff will pass the web-based CITI exam as required by the University of Massachusetts Medical School Institutional Review Board for the Protection of Human Subjects. All project personnel that are engaged in research will have completed the CITI GCP training prior to their involvement in the conduct of the research. In addition, study staff will receive training and supervision regarding patient confidentiality. This training will be directed by Drs. [name] and [name] (co-investigator; informatics). The training will address the rights of patients to keep participation decision (yes or no) and health assessment data private and confidential. Research process training will emphasize patient confidentiality, including procedures for separating patient data from identifying information. Training will also emphasize that discussion or disclosure of any information obtained from research participants during the course of the study is strictly prohibited. Prior to having any direct contact with research participants, the on-site coordinators and the UMMS DCC will receive extensive training in recruitment and assessment procedures.

Only those listed in our IRB application will have access to identified data.

INVESTIGATOR STUDY PLAN

12.14.2021

- Principle Investigator – The PI will be responsible for the overall organization and completion of this study. She will oversee the collaboration with the surgical groups, and to assure patients are enrolled and retained. As supervisor of the data coordinating center at UMass, she will oversee the web-system development (with Co-I for Informatics). She will also collaborate in the analysis and interpretation of the findings, manuscript preparation. Finally, with the Senior Project Principal Investigator: oversees and manages the entire study
- Co-Investigators: assists and advises the PI about the overall study on research procedures and research questions
- Statisticians: Reviews and analyzes study data and produces reports
- Project Director: Manages the Research Coordinators; reviews and adapts the study processes and operations on going; development of process and protocol relating to medical reporting and follow up including medical chart review, surgeon practice review; oversees analysis and dissemination of clinical and research data. Reviews and implements process in regard to retention; contacts study pts/ppts for recruitment, enrollment, follow up, and retention;
- Verbally consents interview subjects and conducts interviews for Aim 1.
- Research Coordinator-A: Screens, recruits, enrolls, follows up with participants and reviews and processes all patient/participant data
- Research Coordinator-B- reviews, processes, all patient/participant data related to the study such as outgoing and ingoing mail, data entry, data reports,follows up with participants for complete data; mails and receives surveys, files, copies participant materials, reviews all materials related to participant medical event reporting and follow up to this such as chart review, surgeon practice review
- Research Assistant-A: mails and receives surveys, files, copies participant materials
- Co-I of Informatics and Research Database Director: develops, updates, manages databases and processes related to the study databases. Oversees all database development and reporting
- Database Developer: develops, updates and tracks databases used for the study under the Informatics and Research Database Director direction

24. LOCAL RECRUITMENT METHODS

SEE #8 ABOVE

26. CONFIDENTIALITY

Aim 1

Participants will be encouraged to not use any identifiers during the interview, including surgeon name, location or their own name. Once interviews have been transcribed, all recording will be destroyed.

Aim 3 Patient Interviews: Identifiers (such as surgeon name, patient name, hospital name) will be removed from transcripts. Audio recordings will be destroyed after all have

INVESTIGATOR STUDY PLAN

12.14.2021

transcribed and all transcripts have been checked for accuracy and deidentified. Original transcripts with identifiers will also be destroyed once all transcripts are checked for accuracy and deidentified.

Confidentiality. The following steps will be taken to insure that all patient data remain confidential. These steps have been used successfully in our prior work.

(a) Use of numeric identifiers: To increase confidentiality, study assessments, including paper data collection forms and electronically stored data will be linked to a unique identifier generated by the programmer.

(b) Data storage: All paper data collection documents will be kept in locked file cabinets within locked offices that are accessible only to the project investigators and staff. Access to the electronic data will be restricted to project investigators and data entry staff. Databases will be password protected to guard against unauthorized access. The servers used for data collection are highly fault-tolerant and are equipped with redundant, hot-pluggable power supplies, redundant network interfaces, and RAID 1/5 hot-pluggable disk storage. Data are encrypted while stored, at a minimum, key sizes of 128 bits for symmetric keys and 1024 bits for asymmetric keys.

(c) Staff training: This training has been the standard of operations for the our previous studies. All project staff have passed the CITI exam on ethical conduct of research. Any newly hired study staff will pass the CITI exam as required by the University of Massachusetts Medical School Institutional Review Board for the Protection of Human Subjects. In addition, study staff will receive training and supervision regarding patient confidentiality. This training will be directed by Drs. [name] and [name]. The training will address the rights of patients to keep participation decision (yes or no) private and confidential. Research process training will emphasize patient confidentiality, including procedures for separating patient data from identifying information. Training will also emphasize that discussion or disclosure of any information obtained from research participants during the course of the study is strictly prohibited. Prior to having any direct contact with research participants, the study coordinator will receive extensive training in recruitment and assessment procedures.

(d) Handling of published data and reports: Published data derived from this study will consist of statistical analyses collapsed (averaged) across participants. Under no circumstances will data from individual participants be identifiable in reports or published manuscripts.

We will use the same IRB approved platform for electronic data collection and storage that is used for previously IRB approved studies. This system includes DatStat for web survey data capture and Cogitas (now called Precision Health) or a UMass IT and privacy approved vendor) for secure data hosting. An overview is summarized below:

Data Transmission

Survey responses are encrypted while in-transit between the patient's browser and our servers using SSL (Secure Sockets Layer) 256 or 128-bit Public Key Encryption. The matter of 256 or 128-bit encryption via SSL is dependent on the browser and the server.

Data Availability

Application and data availability is maintained by redundant servers to insure maximum uptime for all hosted applications.

INVESTIGATOR STUDY PLAN 12.14.2021

Data Backup

Our database backups are conducted on a daily basis. Backups are encrypted and streamed over on a private network to a secure offsite location. Backups are encrypted using 256-bit AES encryption.

Data Access

Physical access to servers and data backup is restricted to a minimal number of IT professionals. Such access is provided only with strong passwords that regularly expire to minimize the chance that inadvertently and unknowingly distributed passwords could cause inappropriate data access. Access to data stored in servers is available only to designated users who log in with specified usernames and complex passwords. Users are logged out after a period of time.

